---

## LIST OF ABBREVIATIONS

Ca-EDTA	Calcium di-sodium Ethylenediamine tetra-acetate
CF	Cystic fibrosis
EDTA	Di-sodium Ethylenediamine tetra-acetate
FEV1	Forced expiratory volume in one second
MetBL	Mettalo-beta-lactamase
mITT	Modified intent to treat
N/A	Not applicable
PsA	Pseudomonas aeruginosa
qPCR	Quantitative PCR
RT-qPCR	Real time quantitative PCR
SAE	Serious adverse event
SOP	Standard operating procedure
DSMC	Data Safety Monitoring Committee
ISF	Investigator Site File
TRIS	Tris(hydroxymethyl)aminomethane

---

**PROTOCOL SYNOPSIS**

TITLE	A Phase IIb, Single-Centre, Randomised, Double-Blind, Comparator-Controlled, Parallel-Group, Pilot Study of Inhaled Tobramycin with added Ca-EDTA vs Tobramycin Alone as Adjunctive therapy to a Course of Standard Treatment for Cystic Fibrosis Children Admitted to Hospital with a Pseudomonas aeruginosa Pulmonary Exacerbation
PRINCIPAL INVESTIGATOR	[name]
CLINICAL PHASE	Phase IIb
OBJECTIVES	The objectives of this study are to assess the efficacy, safety and tolerability of adding Ca-EDTA to inhaled tobramycin when used as adjunctive therapy to a course of intravenous (inpatient) followed by nebulised/oral (outpatient) antibiotics in the treatment of a Pseudomonas aeruginosa pulmonary exacerbation in children with Cystic Fibrosis
METHODOLOGY	Randomised, double-blind, comparator-controlled, parallel group, pilot study
TRIAL POPULATION	Children with Cystic Fibrosis who are infected with Pseudomonas aeruginosa and admitted to hospital for treatment of a pulmonary exacerbation
NUMBER OF PATIENTS	32
ELIGIBILITY CRITERIA	
Inclusion Criteria
 
 
• Male or female children 6 or more years of age with a documented diagnosis of CF (positive sweat chloride test, genotype with two identifiable CF mutations) accompanied by one or more clinical features consistent with the CF phenotype
 
• Current pulmonary exacerbation requiring admission to hospital for intravenous antibiotic therapy
 
• FEV1 <math>\geq</math> 25% of predicted values
 
• Positive sputum or bronchoalveolar lavage culture for Pseudomonas aeruginosa in the previous 12 months
 
• Must be able to give informed consent or have legally acceptable representative who can give informed consent in accordance with ICH/GCP
 
• Females of child-bearing potential must agree to use an acceptable method of contraception for the duration of the trial
 
 
Exclusion Criteria
 
 
• Known hypersensitivity to the investigational product or its components or known relevant medication allergy
 
• Participation in another study with an investigational drug within 2 months of the planned first dose of investigational product
 
• Known relevant substance abuse
 
• Female patients who are pregnant or lactating
 
• Clinically significant disease or other medical condition other than CF or CF-related conditions that would, in the opinion of the Investigator, compromise the safety of the
 

---

**Confidentiality Statement**

This document is confidential and is to be distributed for reference only to study staff, human research ethics committees and the applicable regulatory authorities. Information is not to be reproduced, abstracted or used for sharing of information for any purpose without with the written permission of the [name] or his delegate.

	patient or quality of the data
RANDOMISATION	1:1 investigational product to comparator
INVESTIGATIONAL PRODUCT	
 
• Calcium disodium ethylenediamene tetra acetate (Ca-EDTA) will be supplied as a sterile TRIS-buffered solution in a single-use syringe.
 
• 1.5ml Ca-EDTA solution will be added to 2.5ml Tobramycin solution (Tobra-Day®) and administered via a nebuliser
 
• Final concentration: 50mMol
 
• Dose: 75mg Ca-EDTA
 

REFERENCE THERAPY	
 
• Placebo will be supplied as a sterile Tris-buffered saline solution in a single-use syringe.
 
• 1.5ml placebo solution will be added to 2.5ml Tobramycin solution (Tobra-Day®) to form the comparator, and administered via a nebuliser.
 

DURATION OF TREATMENT	6 weeks (42 days) – 14 days in conjunction with intravenous antibiotics followed by 28 days as outpatient treatment
STUDY DESIGN	See Table of Assessments below
EFFICACY CRITERIA	
Relative to comparator:
 
Primary
 
 
1. Greater reduction in bacterial load
 
 
Secondary
 
 
2. Greater reduction in biofilm mass
 
3. Reduced capacity for PsA to produce biofilm
 
 
Exploratory
 
 
4. Greater reduction in MIC of PsA to Tobramycin and other antibiotics
 
5. Greater clinical improvement (questionnaire and FEV1)
 
6. Greater reduction in evidence of inflammation
 
7. Reduction in beta-lactamase production by PsA
 
8. Differences in lung microbiome
 

SAFETY CRITERIA	
 
• Acute tolerability as measured by respiratory symptoms and signs, as well as FEV1 changes pre-and post-dose.
 
• Systems assessment and vital signs (change pre- and post-dose and change from baseline)
 
• Blood tests – FBC, U&E's, LFT's, Ca and Mg
 
• Treatment emergent adverse events (AE's) up to follow-up visit
 
• Serious Adverse Events (SAE's) up to follow-up visit
 
• Concomitant medications
 
• Monitor PsA virulence factors and microbiome changes
 
 
A DSMC will be established to monitor safety

PHARMACOKINETIC CRITERIA (optional)	Not applicable
STATISTICAL METHODOLOGY	
Demographic data will be displayed and summary statistics will be used to describe the study populations.
 
Efficacy:

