**TABLE OF STUDY ASSESSMENTS**

Visit	While Admitted to Hospital				While At Home		
	Screening	Visit 1	Visit 2	Visit 3 (Discharge)	Visit 4 (TC)	Visit 5 (EoT)	Follow-up (Safety visit)
Days ± visit window	Day - 3 to 1	Day 1	Day 8 ± 3	Day 15 ± 3	Day 29 ± 3	Day 43 ± 3	Day 71 ± 7
Informed consent	x						
Eligibility criteria	x						
Demographics	x						
Medical history	x	x					
Respiratory symptoms check	x	x	x	x	x	x	x
Height and weight	x		x	x		x	x
Vital signs	x		x	x		x	x
Physical exam	x		x	x		x	x
Spirometry	x	x x x 	x x	x x		x	x
Sputum collection	x			x		x	x
Blood collection	x			x		x	x
Concomitant medications	x	x	x	x	x	x	x
CF Questionnaire				x		x	x
Dispense medication		x		x			
Adverse events		x	x	x	x	x	x
First dose of study medication		x					
Patient observation (1/2, 1 and 2 hours post-dose)		x					

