#### Exploratory

1. Greater reduction in MIC of *PsA* to Tobramycin and other antibiotics
2. Greater reduction in evidence of inflammation
3. Reduction in beta-lactamase production by *PsA*
4. Greater clinical improvement (questionnaire and spirometry – FEV1)
5. Change in microbiome

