### **3.2 Endpoints**

#### **3.2.1 Efficacy**

Primary

- Greater reduction in bacterial load relative to comparator

Secondary

- Reduced capacity of *PsA* to produce biofilm relative to comparator
- Reduced biofilm mass relative to comparator

Exploratory

- Greater reduction in MIC of *PsA* to Tobramycin and other antibiotics relative to comparator
- Greater reduction in evidence of inflammation relative to comparator
- Reduction in beta-lactamase production by *PsA*
- Greater clinical improvement relative to comparator (respiratory symptoms check and spirometry – FEV1)
- Differences in microbiome relative to comparator
- 

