**(a) Safety:**

- Ensure patient is willing, fit and able to participate in and likely to complete the study
- Meets eligibility criteria
- Has signed consent
- Has no conditions likely to be complicated by participating in the study
- Treating physician agrees to patient participating in trial
- History, physical assessment, vital signs, spirometry
- Baseline safety blood tests performed

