**(b) Efficacy:**

- **Respiratory symptoms and signs noted**
- **Spirometry recorded**
- **Sputum sample collected**
- **CF Questionnaire applied**

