#### **Confidentiality Statement**

This document is confidential and is to be distributed for reference only to study staff, human research ethics committees and the applicable regulatory authorities. Information is not to be reproduced, abstracted or used for sharing of information for any purpose without with the written permission of the [name] or his delegate.

---

specimen will be homogenised with an equal volume of sputolysin, separated into measured aliquots for each of the specific tests or collection of tests, and stored in appropriate preservative media at -80 degrees centigrade for batch testing once all specimens have been collected. For most of the tests (particular the molecular testing) only very small quantities (50-100 microlitres) are needed.

- **Bacterial load will be assessed by:**
  - **Quantitative PCR (qPCR) using established RT-qPCR assays based on the housekeeping genes *oprL* and *clpX*. These will be performed at the Menzies Institute in Darwin through the Infectious Diseases laboratory at the Telethon Institute of Child Health research, and at [name] laboratory in Queensland.**
  - **CFU counts (bacterial colony forming unit counts) performed in our microbiology laboratory at Princess Margaret Hospital.**

**Routine cultures for clinical assessment (if and as required by the treating physician) will be performed separately and will not be affected by this study.**

- **Biofilm production will be assessed by:**
  - **Imaging techniques using confocal light microscopy using a recently validated procedure at TICHR**
  - **[name]'s laboratory:**
    - **pyoverdinin and pyochelin assays will be used as a measure of iron utilisation in biofilm production.**
    - ***PsA* expression of iron-related virulence genes and RT-qPCR assays based on the housekeeping genes *oprL* and *clpX*.**
    - **In addition, as added insurance to exclude generation of a more aggressive *PsA* as a result of iron starvation, they will be quantifying the transcripts for the following virulence genes: *algD* (alginate synthesis), *hcnB* (cyanogenesis), *lasI* and *rhII* (quorum sensing regulators of biofilm production) and *lasB* (proteolytic enzyme)**
  - **Morphological characteristics of biofilm on culture**
- **Changes in MIC to a range of antibiotics (including particularly Tobramycin) will be done in our laboratory at PMH using standardised commercially available kits.**
- **Clinical comparisons using:**
  - **a standardised CF questionnaire**

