## **7.2 Assessment of Safety**

- Systemic
  - blood tests: FBC, LFT’s, U&E’s, Ca, Mg
  - history and general physical examination (including vital signs) at visits
- Local respiratory:
  - Symptoms – CF questionnaire
  - Symptoms (cough, wheeze and chest tightness) and physical examination (respiratory) at visits pre- and half-hour post-dose
  - Spirometry: change in FEV1 between pre- and half, 1, and 2 hours post-dosing with the first dose, and then pre- and half hour post-dosing at subsequent visits.
- Microbiome:
  - Monitoring of possible changes in *PsA* virulence factors, iron utilization and microbiome as a result of treatment (See paragraph above “Biofilm production assessed ....” In [name] laboratory in Brisbane

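### The CF questionnaire is first given about two weeks after the first study dose, so the questionnaire part of the exploratory clinical-improvement endpoint has no pre-treatment score

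*Protocol*

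**What the plan says.** **Where the questionnaire is an efficacy measure.** The synopsis (Efficacy Criteria, exploratory item 5) gives "Greater clinical improvement (questionnaire and FEV1"), relative to comparator. Section 2.1 repeats it as "Greater clinical improvement (questionnaire and spirometry – FEV1"). Section 7.1 lists "a standardised CF questionnaire" among the clinical comparisons, beside respiratory signs and symptoms and FEV1 change.

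**Where it is not.** Section 3.2.1, the endpoint section, words the same item as "Greater clinical improvement relative to comparator (respiratory symptoms check and spirometry – FEV1"). The questionnaire is not named there.

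**Safety use.** Section 7.2 lists "Symptoms – CF questionnaire" under local respiratory safety. Section 9.1.2 includes the questionnaire among several sources from which adverse events are identified.

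**Schedule.** In the Table of Study Assessments the row "CF Questionnaire" is marked at Visit 3, Visit 5 and Follow-up only. In section 6 the entry "CF Questionnaire applied" first appears at Visit 3 and again at Visits 5 and 6. The Screening list has "History, physical assessment, vital signs, spirometry" and safety bloods, and nothing under efficacy. The Visit 1 pre-dose baseline consists of sputum, a clinical assessment and spirometry. The first study dose is given at Visit 1.

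**The concern.** Improvement needs a starting point. For the questionnaire, the first score comes at discharge, after the two weeks in which intravenous antibiotics are given and study drug is nebulised four times daily (section 3.1). Any difference between arms that arises in those two weeks is already in the first score. If it then stays constant, change from Visit 3 shows nothing.

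The same gap affects the questionnaire as a symptom safety measure: it cannot show worsening from the pre-treatment state. An analysis plan cannot repair this, because the score is never collected. The protocol presents the trial as a pilot to inform later studies (section 10.1.2), so losing the baseline of a patient-level clinical measure costs more than the exploratory label suggests.

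**Working it through.** **Step 1. Read the schedule twice.** The table has seven visit columns.

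| Measure | Screening | V1 | V2 | V3 | V4 | V5 | Follow-up |
|---|---|---|---|---|---|---|---|
| CF questionnaire | – | – | – | x | – | x | x |
| Respiratory symptoms check | x | x | x | x | x | x | x |
| Spirometry | x | x | x | x | – | x | x |

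The visit lists in section 6 give the same questionnaire visits: Visits 3, 5 and 6, and none at Screening, Visit 1 or Visit 2. Two separate parts of the protocol agree, so this is not a table-extraction fault.

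**Step 2. Timing.** The first dose is on Day 1 and the first questionnaire on Day 15 ± 3, that is Day 12 to Day 18. Questionnaires before the first dose: 0. The only within-patient changes available are Visit 3 to Visit 5 and Visit 3 to Follow-up, and both start after the inpatient phase.

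**Step 3. What a baseline would add.** The protocol gives no variance, correlation or power for this endpoint (power is stated only for the primary endpoint), so there is no figure to reproduce. As an illustration, take 16 per arm (synopsis), two-sided 0.05, 80% power, the normal approximation, and an assumed correlation r between baseline and later score. Write SD for the standard deviation of the later score.

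- Comparison of later scores only: detectable difference = (1.960 + 0.842) × √(2/16) = 0.99 SD.
- With baseline as covariate (ANCOVA): the variance is multiplied by 1 − r², so the detectable difference is 0.99 × √(1 − r²) SD and the equivalent sample size is 16/(1 − r²) per arm.

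| Assumed r | 1 − r² | Detectable difference (SD) | Equivalent n per arm |
|---|---|---|---|
| 0.3 | 0.91 | 0.94 | 17.6 |
| 0.5 | 0.75 | 0.86 | 21.3 |
| 0.7 | 0.51 | 0.71 | 31.4 |

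These are large-sample figures that ignore the degree of freedom spent on the covariate.

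**Step 4. Change score or adjustment.** With equal variances, a simple change score has variance 2(1 − r) relative to the later score alone: 1.4, 1.0 and 0.6 at r = 0.3, 0.5 and 0.7. A raw change score is therefore less precise than later scores alone when r is below 0.5. The gain in Step 3 comes from using the baseline as a covariate.

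**The case against.** Five points can be made on the other side.

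- **Only one measure is affected.** A reader might infer that clinical improvement from the exacerbation cannot be measured at all. The protocol does not support that. Spirometry and the respiratory symptoms check are scheduled before the first dose, so two of the three clinical comparisons in section 7.1 have a baseline. On the wording of section 3.2.1, the endpoint does not use the questionnaire and lacks nothing. This stands, and it turns part of the point into an inconsistency over the instrument.
- **Safety is covered elsewhere.** A reader might also infer that inpatient worsening would go unseen. It would not: symptom checks, spirometry, diary cards and adverse-event review run through Visits 1 to 3, and detecting adverse events from a questionnaire does not require a pre-treatment score. This stands. What remains is that the questionnaire itself contributes nothing on change from the pre-treatment state.
- **Randomisation protects the comparison.** Later scores compared between arms are unbiased, and chance imbalance at baseline is already reflected in the standard error. This stands. The loss is in precision and in meaning: the comparison is of level, not improvement. Baseline FEV1 or symptom data could serve as substitute covariates, though neither is the questionnaire score.
- **The gain may be small.** The correlation between a score during an acute exacerbation and one taken weeks later could be low. At r = 0.3 the gain is under two patients per arm. This stands, and the range shown includes it.
- **The Visit 1 clinical assessment might include the questionnaire.** This does not persuade. The questionnaire is named explicitly at every visit where it is given, and its Visit 1 cell in the table is blank.

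**Conclusion.** The point holds for the questionnaire component only. On the schedule as written, no patient has a questionnaire score before the first dose. Questionnaire change from the exacerbation therefore cannot be calculated, and change from Visit 3 omits the inpatient phase. A between-arm comparison of later scores remains valid and unbiased, but it measures level and cannot be adjusted for the starting score.

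Separately, section 3.2.1 names the respiratory symptoms check where the synopsis and sections 2.1 and 7.1 name the questionnaire. These must be reconciled, because the choice decides whether the stated endpoint has a baseline.

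The precision at stake runs from slight (equivalent to 17.6 rather than 16 per arm) to substantial (about 31 per arm), and depends wholly on an assumed correlation of 0.3 to 0.7. Severity is low: this is one component of one exploratory endpoint, and the primary and secondary endpoints are untouched. It is still worth correcting, because a baseline missed for an enrolled patient cannot be recovered.

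**What to change.** 1. Add the CF questionnaire at Screening or at Visit 1, before the first study dose, in both the Table of Study Assessments and section 6.
2. Analyse the Visit 3, Visit 5 and Follow-up scores with the pre-dose score as a covariate (ANCOVA), in preference to a raw change score.
3. Name the same instrument or instruments for clinical improvement in the synopsis and in sections 2.1, 3.2.1 and 7.1.
4. For any patients already enrolled without a pre-dose score, report later scores as between-arm comparisons of level and do not describe them as improvement.

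The cost is one further administration per patient of an instrument the trial already uses. The protocol does not state its length, so the added time cannot be given.

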**Confidentiality Statement**

This document is confidential and is to be distributed for reference only to study staff, human research ethics committees and the applicable regulatory authorities. Information is not to be reproduced, abstracted or used for sharing of information for any purpose without with the written permission of the [name] or his delegate.

	
 
The first aim would be to establish the standard deviation of within-subject variations. If this standard deviation proves to be similar to previous studies, 32 patients (16 in each group) study will have an 80% power of detecting a difference in the primary efficacy endpoint to the 0.05 level of significance. If not similar, the standard deviation found in our population will guide us as to required numbers for future Phase III studies to demonstrate efficacy.
 
 
Safety:
 
 
Acute changes in respiratory and systemic symptoms and signs, PFTs, and blood parameters will be summarised, with categorical analysis of clinically significant findings.          All reported AE's will be coded and grouped by body system. AE's will be tabulated by treatment group and sorted by body system. The incidence of AE's in each treatment group will be tabulated by seriousness, severity and relationship to investigational product.
 
Concomitant medication use will be summarised.
 

TRIAL SITE	Princess Margaret Hospital for Children

**TABLE OF STUDY ASSESSMENTS**

Visit	While Admitted to Hospital				While At Home		
	Screening	Visit 1	Visit 2	Visit 3 (Discharge)	Visit 4 (TC)	Visit 5 (EoT)	Follow-up (Safety visit)
Days ± visit window	Day - 3 to 1	Day 1	Day 8 ± 3	Day 15 ± 3	Day 29 ± 3	Day 43 ± 3	Day 71 ± 7
Informed consent	x						
Eligibility criteria	x						
Demographics	x						
Medical history	x	x					
Respiratory symptoms check	x	x	x	x	x	x	x
Height and weight	x		x	x		x	x
Vital signs	x		x	x		x	x
Physical exam	x		x	x		x	x
Spirometry	x	x x x 	x x	x x		x	x
Sputum collection	x			x		x	x
Blood collection	x			x		x	x
Concomitant medications	x	x	x	x	x	x	x
CF Questionnaire				x		x	x
Dispense medication		x		x			
Adverse events		x	x	x	x	x	x
First dose of study medication		x					
Patient observation (1/2, 1 and 2 hours post-dose)		x					

**TC = Telephone Call; EoT = End of Treatment**

 At visit 1, spirometry will be performed pre-dose and at ½, 1 and 2 hours post-dose

 At visits 2 and 3, spirometry will be performed pre-dose and post-dose

## 1. BACKGROUND INFORMATION

### 1.1 Introduction

Cystic fibrosis (CF) individuals are highly susceptible to chronic lung infection by the opportunistic environmental bacteria *Pseudomonas aeruginosa* (*PsA*). This organism is thought to persist by forming biofilms within the relatively hypoxic mucous of the CF lung. Once established, biofilm dwelling bacteria are virtually impossible to eradicate with existing therapies. For some time now it has been recognised that iron is essential not only for growth and proliferation of *PsA*, but also for biofilm creation by the *PsA*. In the CF lung (both in epithelial cells and the surrounding mucous) there is increased iron compared to non CF lungs creating an environment conducive to both *PsA* proliferation and biofilm formation. In the light of this, [name], Moreau-Marquis, and others, have looked at strategies to interfere with *PsA* iron homeostasis on the basis that this would lead to inhibition of biofilm formation thus rendering the *PsA* more vulnerable to eradication with antibiotics. One strategy involves the use of heavy metal chelators which bind available iron making it unavailable to *PsA*. EDTA in particular is a well-known and safe heavy metal chelator which by its iron chelating properties has been shown to be very effective in inhibiting biofilm production both in vivo and in vitro. As predicted, this in turn has led to markedly reduced minimal inhibitory concentration (MIC) of the *PsA* for a number of antibiotics (including Tobramycin) and a marked increase in killing of the organism in vitro. Importantly, this effect has been shown to be present in low, normal and increased iron environmental circumstances and also in both aerobic and anaerobic conditions. One *in vitro* study showed that the addition of EDTA-Tris to gentamicin improved killing of *PsA* by 1000-fold more than treatment with only gentamicin.

In the clinical setting, the veterinary world has for many years recognised the effectiveness of combining EDTA with Tobramycin (as well as certain other antibiotics). Chronic *PsA* infection causing persistent discharging ears in dogs, and sinusitis and endometritis in horses, which has failed to be eradicated with prior aggressive antibiotic use, has been successfully cleared in all reported instances by addition of EDTA to antibiotic irrigation solutions. As a result of this unequivocal increase in benefit, the combination has now become standard best practice in veterinary guidelines. Human studies have been slow to pick up on this benefit. In 1984 Hillman reported using nebulised (aerosolised) Ca-EDTA in combination with an intravenous antibiotic (Penicillin) in four intubated and ventilated non-CF ICU patients with *PsA* lung infection where prior treatment with a conventional anti-*PsA* antibiotic (Ticarcillin) had failed to clear the organism. Forty-eight hours after starting the nebulisation of the Ca-EDTA, the *PsA* was eradicated in all four patients with no recurrences subsequently and no reported side effects. The natural progression from all of this is to consider using the combination of EDTA with nebulised antibiotics (particularly Tobramycin) in CF patients chronically colonised with *PsA* to see if this will achieve the same result. The hypothesis being that the iron chelating effect of EDTA will result in reduction in biofilm production thereby rendering the *PsA* more vulnerable to antibiotic exposure and thus hopefully leading to improved bacterial killing of the organism and possibly eradication. This study has been designed to attempt to prove this hypothesis.

An additional mechanism by which heavy metal chelators may improve effectiveness of antibiotics against *PsA* has also been recently reported. Certain *PsA* produce metallo-beta-lactamase (MetBL), an enzyme that neutralises the effect of beta-lactam antibiotics commonly used to treat *PsA* infection. One study in mice showed that nebulised Ca-EDTA, by its zinc chelating effect, resulted in inhibition of the MetBL thus rendering these *PsA* more susceptible to the antibiotics. The same study showed that in addition, EDTA (by this same zinc-chelating effect) also neutralised other tissue-damaging *PsA*-produced metallo-proteases, which contribute to airway inflammation.

---

